1.4.1. Safety

As of September 27, 2020, 330 patients were treated in the LOXO-BTK-18001 study and received LOXO-305. This includes 324 patients treated at doses ranging from 25 mg QD to 300 mg QD in Phase 1/2 Monotherapy cohorts, and 6 patients treated in Phase 1b Combination Arm A (LOXO-305 200 mg QD plus venetoclax 400 mg QD [after venetoclax ramp-up]). A full summary of treatment-emergent adverse events (TEAEs) for patients in the study is provided in the LOXO-305 IB and the Investigator is directed to the safety information described in that document.¹ A summary of safety for LOXO-305 given as monotherapy to patients in the LOXO-BTK-18001 study is provided below.

- In the 324 patients in the Phase 1/2 Monotherapy cohorts, TEAEs reported in $\geq 10\%$ of patients (n = 33 or more) were fatigue (20.1% total, 8.3% related), diarrhea (17.0% total, 8.6% related), and contusion (13.0% total, 9.0% related). Drug-related TEAEs were reported in 156 of 324 patients (48.1%) in the Phase 1/2 Monotherapy cohorts. The most frequently reported drug-related TEAEs for LOXO-305 (those in $> 5\%$ of patients overall) were contusion (9.0%), diarrhea (8.6%), and fatigue (8.3%). All other drug-related TEAEs were reported in $< 5\%$ of patients (ie, < 17 patients each). Treatment-emergent AEs of severity Grade 3 or 4 were reported in 87 of 324 patients (26.9%) in the Phase 1/2 Monotherapy cohorts, with 41 (12.7%) of these Grade 3 or 4 AEs reported as related to study drug.
- On-study death (death within 28 days of the last dose of study drug) due to a Grade 5 (fatal) AE was reported in 4 of 324 patients (1.2%) in the Phase 1/2 Monotherapy cohorts. One Grade 5 AE, *Enterococcus faecium*-related septic shock, was considered to be related to study drug (further details are provided in the LOXO-305 IB¹). All other Grade 5 AEs were considered to be not related to study drug; these included pneumonia fungal, shock, and pleural effusion.

Treatment-emergent AEs reported following LOXO-305 administration in healthy volunteers in the LOXO-BTK-20014 study (headache, nausea, and vomiting), were all Grade 1 in severity and considered to be related to LOXO-305. All 3 events were reported by 1 subject and resolved within 1 to 1.5 days.

Treatment-emergent AEs reported following LOXO-305 administration in healthy volunteers in the LOXO-BTK-20006 study (intermittent belching, bloating, insect bite, aphthous ulcer, nausea, intermittent diarrhea [x2], muscle twitch), were all Grade 1 in severity, and bloating, 1 instance of intermittent diarrhea, and intermittent belching were considered to be related to LOXO-305 and rifampin. All 7 AEs were reported by 3 subjects and all events resolved prior to End of Treatment (EOT; preliminary data on file at the time of this protocol's development).

Treatment-emergent AEs reported following LOXO-305 administration in healthy volunteers in the LOXO-BTK-20017 study (headache [observed at the 300 mg LOXO-305 dose], and headache [x2], intermittent headache, and petechial rash left thigh [observed at the 900 mg LOXO-305 dose]), were all Grade 1 in severity. One instance of headache observed at the 300 mg LOXO-305 dose and 1 instance observed at the 900 mg LOXO-305 dose, the intermittent headache, and the petechial rash left thigh were considered to be related to LOXO-305. All five AEs were reported by 4 subjects and resolved within 2 hours to 5 days of onset (preliminary data on file at the time of this protocol's development).

Treatment-emergent AEs reported following LOXO-305 administration in healthy volunteers in Part 1 of the LOXO-BTK-20007 study (bloody nose, headache, loose stool [x2], red bumps on left knee, small abrasion to right elbow), were all Grade 1 in severity and headache was considered to be related to LOXO-305. All 7 AEs were reported by 4 subjects and all events resolved within 1 to 2 days (preliminary data on file at the time of this protocol's development).

Treatment-emergent AEs reported following LOXO-305 administration in healthy volunteers in Part 2 of the LOXO-BTK-20007 study (tenderness at left venipuncture site [x2], bruising to left antecubital secondary to phlebotomy [x2], bruising to right antecubital secondary to phlebotomy, and allergic reaction), were all Grade 1 in severity and no events were considered to be related to LOXO-305. All 6 AEs were reported by 4 subjects and all events resolved within 1 to 2 days (preliminary data on file at the time of this protocol's development).

Treatment-emergent AEs reported following LOXO-305 administration in healthy volunteers in the LOXO-BTK-20008 study (injection site pain, nasal congestion, flatulence, constipation, increased urinary frequency, facial rash, and skin tear from tape at IV site), were all Grade 1 in severity, and flatulence, constipation, and increased urinary frequency were considered to be related to LOXO-305. All 7 AEs were reported by 3 subjects and all events resolved within 1 to 8 days (preliminary data on file at the time of this protocol's development).

As part of each clinical trial conducted in patients or healthy volunteers, ECG and vital signs are performed at intervals specified by protocol. For study LOXO-BTK-18001 conducted in patients, no clinically significant findings of QTc prolongation have been identified in 330 patients as of September 27, 2020 (LOXO-305 IB¹). In addition, there have been no clinically significant abnormal findings in vital signs and ECG data in the studies investigating LOXO-305 conducted in healthy volunteers as of November 23, 2020 (preliminary data on file at the time of this protocol's development).

1.4.2. Pharmacokinetics

As of September 30, 2020, PK data were available from 181 patients enrolled in the LOXO-BTK-18001 study. Steady-state PK parameters of LOXO-305 in these cancer patients could be derived from data collected on Cycle 1 Day 8 (Figure 1), and are shown in Table 1. These data show that LOXO-305 is absorbed after oral administration with a median time to maximum observed plasma concentration (t_{max}) of approximately 2 hours and low clearance (Table 1). Due to the limited sampling interval (0-8 hours), imputation for the 24-hour sample was made from Cycle 1 Day 8 predose sample, leading to an estimated plasma half-life of

approximately 20 hours. Maximum observed plasma concentration and area under the plasma concentration-time curve (AUC) of LOXO-305 showed increase proportional to dose (Figure 2). Following administration of the recommended Phase 2 dose (RP2D) 200 mg QD, mean trough plasma levels of LOXO-305 exceeded the concentration required for 96% inhibition of BTK in vitro ($IC_{50} = \text{[CC]} \text{ ng/mL}$, $IC_{96} = \text{[CC]} \text{ ng/mL}$). Further details may be found in the IB.¹

Pharmacokinetic data following oral administration of a 200-mg dose of LOXO-305 in tablet form in healthy volunteers in the LOXO-BTK-20014 study indicate that there was little effect of either a standard meal or the proton pump inhibitor omeprazole on the PK of LOXO-305.

**Table 1: Pharmacokinetic Parameters of LOXO-305 in Cancer Patients
(Study LOXO-BTK-18001) at Steady State (Cycle 1 Day 8)**

[figure not shown]
Dose Level	N	C_{\max} (ng/mL) Geo mean (%CV)	t_{\max} (h) Median (min, max)	AUC_{0-8} (ng*h/mL) Geo mean (%CV)	AUC_{0-24} (ng*h/mL) Geo mean (%CV)	CL/F (L/h) Geo mean (%CV)	$t_{1/2}$ (h) Geo mean (%CV)	Ratio AUC_{0-8} Day 8/Day 1 Geo mean (%CV)
25 mg QD	5	734 (11.0%)	2 (1, 8)	4240 (12.4%)	9800 (25.8%)	1.55 ^a (69.6%)	18.2 ^a (60.1%)	1.44 (23.0%)
50 mg QD	6	1420 (19.2%)	1.5 (1, 4)	8660 (24.7%)	20100 (34.9%)	2.62 ^b (36.7%)	17.6 ^b (39.6%)	1.51 (25.9%)
100 mg QD	9	3910 (35.6%)	2 (1, 4)	22000 (37.2%)	52400 (39.7%)	0.968 ^c (63.0%)	22.2 ^c (33.9%)	1.88 (42.8%)
150 mg QD	20	4680 (29.1%)	2 (1, 8)	28000 (29.6%)	64400 (39.6%)	1.36 ^d (66.7%)	18.1 ^d (51.8%)	1.74 (24.9%)
200 mg QD	99	5770 (47.7%)	2 (1, 8)	36900 (40.8%)	91000 (42.0%)	1.14 ^e (61.8%)	19.9 ^e (56.2%)	1.69 ^h (29.6%)
250 mg QD	25	8100 (28.1%)	2 (1, 4)	49700 (31.3%)	111000 (38.7%)	1.26 ^f (1.08%)	17.4 ^f (50.6%)	1.68 (24.5%)
300 mg QD	17	10700 (26.6%)	2 (1, 4)	65800 (35.9%)	158000 (49.2%)	1.63 ^g (42.5%)	30.1 ^g (102%)	2.15 (31.2%)

Abbreviations: AUC_{0-8} = area under the concentration-time curve from time 0 to 8 hours; AUC_{0-24} = area under the concentration-time curve from time 0 to 24 hours; CL/F = apparent oral clearance; C_{\max} = maximum drug concentration; Geo mean = Geometrical mean; N = number of subjects; QD = once daily; CV = coefficient of variation; $t_{1/2}$ = half-life; t_{\max} = time of maximal plasma concentration.

[figure not shown]
^a N= 4, ^b N= 5, ^c N= 8, ^d N= 18, ^e N= 64, ^f N= 21, ^g N= 16, ^h N= 73

SDTM Transfer: September 30, 2020

CCI

CCI

SDTM Transfer: September 30, 2020

Preliminary and interim plasma concentration data from ongoing study LOXO-BTK-20008 indicate that the dose of 200 mg QD in healthy volunteers produces a LOXO-305 steady-state geometric mean C_{max} of **CCI** ng/mL and AUC from hour 0 to 24 hours postdose (AUC₀₋₂₄) of approximately **CCI** ng*h/mL. These results indicate that the dose of 200 mg QD in this study will provide exposure in the range of the RP2D of LOXO-305 seen in patients, while remaining well under the no observed adverse effect level C_{max} for genotoxicity of approximately **CCI** ng/mL.

1.5. Study Rationale

The objective of DDI studies is to determine whether potential interactions between an investigational drug and other drugs exist. Drug-drug interaction studies have an important role in drug development,⁹ and this study is being performed as part of the development program for LOXO-305.

LOXO-305 showed no detectable inhibition (IC_{50} **CCI** μ M) of CYP1A2, CYP2B6, CYP2C19, and CYP2D6, and weak inhibition of CYP2C8, CYP2C9, and CYP3A4 with inhibitory constant (K_i) values ranging from **CCI** μ M in human liver microsomes. After pre-incubation of microsomes with LOXO-305 and nicotinamide adenine dinucleotide phosphate for 30 minutes prior to addition of CYP450 probe substrate, the CYP3A4 inhibitory potency of LOXO-305 was increased, suggesting the potential for time-dependent inhibition of CYP3A4. Further kinetic evaluation confirmed that LOXO-305 is a time-dependent inhibitor of CYP3A4 with a K_i value of **CCI** μ M and a k_{inact} (maximal inactivation rate constant) value of **CCI** $.15\text{ h}^{-1}$ resulting in a C_{inact} value (inactivation clearance) of $8.64\text{ min}^{-1}\text{ mM}^{-1}$.

In an in vitro hepatocyte assay, LOXO-305 induced mRNA for CYP3A4, CYP3A5, CYP2B6, and CYP2C19. For both CYP2B6 and CYP2C19, an increase in activity was seen. For CYP3A4, LOXO-305 did not cause an increase in activity, likely due to concurrent inhibition of CYP3A4 by LOXO-305. LOXO-305 caused a decrease in mRNA for CYP1A2 but did not lead to a reduction of CYP1A2 activity. In the study, CYP2D6, CYP2C8, and CYP2C9 mRNA were not induced.

LOXO-305 may have the potential to raise plasma concentrations of drugs that are substrates of CYP2C8, CYP2C9, and CYP3A4 or lower plasma concentrations that are metabolized by CYP1A2, CYP2B6, CYP2C19, or CYP3A4. This study is designed to determine the effect of LOXO-305 on the PK of caffeine (CYP1A2 substrate), S-warfarin (CYP2C9 substrate), and omeprazole (CYP2C19 substrate). The effects of LOXO-305 on the PK of other CYP450 substrates will be explored in separate clinical studies. Caffeine, warfarin, and omeprazole are commonly used as index substrates for CYP450 enzymes in DDI studies.⁹

1.6. Risk Assessment

Subjects in the current study will not receive any health benefit (beyond that of an assessment of their medical status) from participating in the study. The risks of participation are primarily those associated with adverse reactions to the study treatments, although there may also be some discomfort from collection of blood samples and other study procedures. The dose of LOXO-305 administered in this study is not anticipated to induce any potential risk to subjects participating in this study as the dose does not exceed the highest dose safely administered in first-in-human study or healthy volunteer studies.¹ More information about the known and expected benefits, risks, and reasonably anticipated AEs associated with LOXO-305 may be found in the IB.¹

There is a potential risk that multiple doses of LOXO-305 may lead to decreases in white blood cells including neutrophils, lymphocytes, monocytes, and eosinophils. Therefore, to mitigate any potential immunosuppressive risks during the ongoing SARS-CoV-2 (COVID-19) pandemic, subjects will remain in the Clinical Research Unit (CRU) for 96 hours postdose (Day 23) to allow for LOXO-305 elimination. In addition, subject's hematology laboratory results will be reviewed prior to discharge from the CRU. More information about the known and expected benefits, risks, and reasonably anticipated AEs associated with LOXO-305 may be found in the IB.¹

The dose of caffeine, omeprazole, vitamin K, and warfarin administered in this study are not anticipated to induce any potential risk or benefit to subjects participating in this study, as they are single doses administered according to the dosing recommendations in the full prescribing information.

The safety monitoring practices employed will include AE reporting, vital sign measurements, 12-lead ECGs, clinical laboratory evaluations, and physical examinations, and are considered adequate to protect the subjects' safety.

2. OBJECTIVES AND ENDPOINTS

2.1. Objectives

2.1.1. Primary Objective

The primary objective of the study is to assess the effect of multiple oral doses of LOXO-305 on the PK of single oral doses of caffeine (CYP1A2 substrate), S-warfarin (CYP2C9 substrate), and omeprazole (CYP2C19 substrate) in healthy subjects.

2.1.2. Secondary Objective

The secondary objective of the study is to assess the safety and tolerability of multiple oral doses of LOXO-305 when administered alone, and coadministered with a single oral dose of probe drug cocktail.

2.2. Endpoints

2.2.1. Primary Endpoints

The following PK parameters will be calculated whenever possible, based on the plasma concentrations of caffeine/paraxanthine, omeprazole, S-warfarin, and LOXO-305 (as appropriate):

- AUC_{0-24}
- AUC from hour 0 to the last measurable concentration (AUC_{0-t})
- AUC from hour 0 extrapolated to infinity ($AUC_{0-\infty}$)
- percentage extrapolation for $AUC_{0-\infty}$ (% AUC_{extrap})
- apparent systemic clearance (CL/F)
- apparent plasma terminal elimination half-life ($t_{1/2}$)
- C_{max}
- t_{max}
- apparent terminal elimination rate constant (λ_z)
- apparent volume of distribution at the terminal phase (V_z/F)
- mean residence time (MRT)
- AUC_{0-24} and AUC_{0-48} ratio of paraxanthine to caffeine (MRAUC; caffeine/paraxanthine only).

2.2.2. Secondary Endpoints

Safety and tolerability will be assessed by monitoring AEs, performing physical examinations and clinical laboratory evaluations, measuring vital signs, and recording 12-lead ECGs.

3. INVESTIGATIONAL PLAN

3.1. Overall Study Design and Plan

This is a Phase 1, open-label, 2-period, fixed-sequence DDI study to investigate the effect of multiple oral doses of LOXO-305 on the PK of single oral doses of caffeine (CYP1A2 substrate) and its metabolite paraxanthine, S-warfarin (CYP2C9 substrate), and omeprazole (CYP2C19 substrate) in healthy subjects.

In Period 1, Day 1, 200 mg caffeine (tablet), 40 mg omeprazole (capsule), and 10 mg warfarin (tablet) administered as a single dose of probe drug cocktail, along with 10 mg vitamin K (tablets), will be administered in the morning following a fast of at least 10 hours predose and 2 hours postdose. Blood samples for concentrations of the substrates (caffeine/paraxanthine, omeprazole, and S-warfarin) in plasma will be collected CCI [REDACTED]. Of the samples collected for concentrations of each substrate in plasma CCI [REDACTED], samples will be analyzed for concentration of caffeine/paraxanthine from CCI [REDACTED], for concentration of omeprazole from CCI [REDACTED], and concentrations of S-warfarin from CCI [REDACTED].

There will be a washout period of 5 days between administration of the probe drug cocktail on Day 1 and the first dose of LOXO-305 on Day 6.

In Period 2, on Days 6 through 19, oral doses of 200 mg LOXO-305 will be administered QD for 14 consecutive days in the morning at the actual time of the Day 1 probe drug cocktail dosing (\pm 1 hour). On Day 15, LOXO-305 will be coadministered with 200 mg caffeine (tablet), 40 mg omeprazole (capsule), and 10 mg warfarin (tablet) administered as a single dose of probe drug cocktail, along with 10 mg of vitamin K (tablets) at the actual time of the Day 1 probe drug cocktail dosing (\pm 1 hour) following a fast of at least 10 hours predose and 2 hours postdose. On Days 7 through 11, and Days 13, 14, 16, 18, and 19, subjects will fast for at least 2 hours predose and 1-hour postdose. On Days 6, 12, and 17 where clinical laboratory evaluations are performed, subjects will fast for at least 8 hours predose and 1 hour postdose. Blood samples for concentrations of LOXO-305 in plasma will be collected and analyzed CCI [REDACTED].

[REDACTED] Blood samples for concentrations of the substrates (caffeine/paraxanthine, omeprazole, and S-warfarin) in plasma CCI [REDACTED]. Of the samples collected for concentrations of each substrate in plasma predose CCI [REDACTED], samples will be analyzed for concentration of caffeine/paraxanthine CCI [REDACTED], for concentration of omeprazole CCI [REDACTED], and for concentration of S-warfarin CCI [REDACTED].

[figure not shown]
The schematic of the study design is displayed in [Figure 3](#). The start of the study is defined as the date the first subject who is enrolled in the study signs an Informed Consent Form (ICF). Note that enrolled subjects are defined as those subjects who are assigned to receive a dose of study drug; this definition excludes screen failure subjects. Replacement subjects may be enrolled only if deemed necessary by the Sponsor.

Subjects who are determined to be screen failures are permitted to be re-screened if the Investigator (or designee), with agreement from the Sponsor, feels that the subject may meet eligibility criteria upon re-screen. Re-screened subjects will be provided a new subject number.

To assess their eligibility to enter the study, potential subjects will be screened within 34 days (Days -35 to -2) and be admitted to the CRU on Day -1 (Check-in).

Subjects will be confined at the CRU from the time of Check-in (Day -1) until EOT on Day 23 upon completion of all PK and safety assessments or Early Termination (ET) if the subject discontinues. Dosing of probe drug cocktail will occur on Day 1 and Day 15 and dosing of LOXO-305 will occur on Days 6 through 19. A follow-up phone call will occur for all subjects who received at least 1 dose of study drug (including subjects who are terminated early) 7 days (\pm 2 days) after EOT or ET. The duration of participation is expected to be approximately 67 days (Screening through follow-up phone call).

Figure 3: Study Schematic

Abbreviations: EOT = End of Treatment; ET = Early Termination; ICF = Informed Consent Form; PK = pharmacokinetic.

In this study, physical examinations, 12-lead ECGs, vital sign measurements, How Do You Feel? (HDYF?) inquiries, clinical chemistry panel, coagulation parameters, hematology panel, urinalysis (UA; [Appendix 2](#)), and recording of concomitant medications will be performed at specified times during the study (for specific timepoints and details on each study variable, refer to [Appendix 4](#)).

Adverse events and serious adverse events (SAEs) will be collected beginning at informed consent. Adverse events will be reported throughout the study (ie, from signing of the ICF until End of Study [EOS], or until ET if the subject discontinues from the study and does not complete a follow-up phone call), either as subject medical history (if the event is reported as beginning prior to signing of the ICF or if the event occurs prior to study drug administration on Day 1 and is assessed as not related to study procedures by the Investigator [or designee]) or as AEs (if the event occurs after signing of the ICF but prior to study drug administration on Day 1 and is assessed as related to study procedures by the Investigator [or designee], or if the event occurs after study drug administration on Day 1 through EOT or ET regardless of relationship to study drug). From EOT or ET through EOS, only AEs assessed as related to study drug by the Investigator (or designee) are to be reported. All SAEs that develop from

the time of ICF signing until EOS (or ET, if the subject discontinues from the study and does not complete a follow-up phone call) are to be reported.

A Schedule of Assessments is presented in [Appendix 4](#). Study completion is defined as the time of the last subject's follow-up phone call.

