7.3.1. Adverse Events

Adverse event definitions; assignment of severity, causality, action taken, and outcome; and procedures for reporting SAEs are detailed in [Appendix 1](#).

Subjects will be asked a non-leading HDYF? question such as “Have there been any changes in your health status since Screening/since you were last asked?” at the timepoints specified in [Appendix 4](#) (ie, at Screening [after the ICF is signed], at Check-in [Day -1], at each postdose vital sign measurement, and at an appropriate time for all other days). Subjects will also be encouraged to voluntarily report AEs occurring at any other time through the EOS.

Adverse events, whether volunteered, identified by the subject’s responses to HDYF? inquiries, or noted on physical examination, ECG, vital sign measurements, or clinical laboratory evaluations, will be recorded throughout the study (ie, from signing of the ICF until EOS [or ET if the subject discontinues from the study and does not complete a follow-up phone call]), either as subject medical history (if the event is reported as beginning prior to signing of the ICF or if the event occurs prior to study drug administration on Day 1 and is assessed as not related to study procedures by the Investigator [or designee]) or as AEs (if the event occurs after signing of the ICF but prior to study drug administration on Day 1 and is assessed as related to study procedures by the Investigator [or designee], or if the event occurs after study drug administration on Day 1 through EOT or ET regardless of relationship to study drug). From EOT or ET through EOS, only AEs assessed as related to study drug by the Investigator (or designee) are to be reported. All SAEs that develop from the time of ICF signing until EOS (or ET, if the subject discontinues from the study and does not complete a follow-up phone call) are to be reported.

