Unless a subject withdraws consent or is withdrawn from the study and does not complete the follow-up phone call, all subjects must be followed until EOS. Subjects with AEs that are assessed as related to study drug by the Investigator (or designee) which are ongoing at EOS may continue to be followed until the symptoms or value(s) return to normal, or acceptable levels, as judged by the Investigator (or designee) and confirmed by the Sponsor. The Investigator (or designee) should use appropriate judgment in ordering additional tests as necessary to monitor the resolution of events. The Sponsor may request that additional safety tests be performed.

Subjects will receive a follow-up phone call 7 days (\pm 2 days) after EOT or ET to determine if any SAE or drug-related AE has occurred since the EOT or ET visit.

At all times, a subject may be required to remain at the CRU for longer at the discretion of the Investigator (or designee).

Any event that meets the criteria of a suspected unexpected serious adverse reaction (SUSAR) will be reported to the Institutional Review Board (IRB) according to CRU policy by the Investigator (or designee) and to regulatory authorities by the Sponsor (or Sponsor designee) according to regulatory authority requirements. Refer to Reference Safety Information in the current [IB¹](#) for LOXO-305 for additional safety information.

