The Investigator (or designee) will make a determination of the relationship of the AE to the study drug using a 2-category system according to the following guidelines:

- **NOT RELATED** = The time course between the administration of investigational product and the occurrence or worsening of the AE rules out a causal relationship and another cause (eg, concomitant drugs, therapies, complications, comorbidities) is suspected
- **RELATED** = The time course between administration of investigational product and the occurrence or worsening of the AE is consistent with a causal relationship and no other cause (eg, concomitant drugs, therapies, complications, comorbidities) can be identified

An AE is associated with the use of the drug if there is a reasonable possibility that the experience may have been caused by the drug.

Pregnancy

As information is available, a pregnancy (including pregnancy in female partners of male subjects) diagnosed through End of Study (EOS) or Early Termination (ET; if the subject discontinues from the study and does not complete a follow-up phone call) and for up to 90 days after study drug administration on Day 19 (or last administration of study drug if subject terminates from the study early) should be reported by the Investigator (or designee) via email to Covance or the Sponsor's Clinical Safety Representative within 24 hours of being notified. Covance or the Sponsor's Clinical Safety Representative will then forward the Pregnancy Form to the Investigator (or designee) for completion.

email: [contact]

A subject becoming pregnant while on study drug will immediately be withdrawn from the study and ET study procedures will be performed. The subject or partner should be followed by the Investigator (or designee) until completion of the pregnancy. If the pregnancy ends for any reason before the anticipated date, the Investigator (or designee) should notify Covance or the Sponsor's Clinical Safety Representative. At the completion of the pregnancy, the Investigator (or designee) will document the outcome of the pregnancy. If the outcome of the pregnancy meets the criteria for immediate classification as a serious adverse event (SAE; ie, postpartum complication, spontaneous abortion, stillbirth, neonatal death, or congenital anomaly), the Investigator (or designee) should follow the procedures for reporting an SAE.

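### After release from the unit, non-serious AEs are recorded only if judged related, under an inconsistent definition of related, and the SAP pools them with all-cause AEs

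*Protocol*

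**What the plan says.** Protocol section 3.1 sets two recording regimes. From Day 1 dosing an event is an AE "if the event occurs after study drug administration on Day 1 through EOT or ET regardless of relationship to study drug". After that: "From EOT or ET through EOS, only AEs assessed as related to study drug by the Investigator (or designee) are to be reported". The same rule stands in the synopsis, section 7.3.1, Appendix 4 footnote j and SAP section 4. Serious events are exempt from the filter; section 7.3.1 requires reporting of "All SAEs that develop from the time of ICF signing until EOS".

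The only scheduled contact after release is a phone call 7 (±2) days after EOT or ET. Section 7.3.1 gives its purpose as "to determine if any SAE or drug-related AE has occurred since the EOT or ET visit", and Appendix 4 footnote v says the same in substance. Section 7.3.1 also encourages subjects to volunteer AEs through EOS.

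Section 1.6 states the risk: "There is a potential risk that multiple doses of LOXO-305 may lead to decreases in white blood cells including neutrophils, lymphocytes, monocytes, and eosinophils". It ties this to immunosuppression during the pandemic and answers it with confinement to Day 23 and a haematology review before discharge.

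Appendix 1 has two causality categories. RELATED needs a consistent time course and that "no other cause (eg, concomitant drugs, therapies, complications, comorbidities) can be identified". NOT RELATED needs a time course that "rules out a causal relationship and another cause (eg, concomitant drugs, therapies, complications, comorbidities) is suspected". A further sentence, cut here before its last word, reads: "An AE is associated with the use of the drug if there is a reasonable possibility that the experience may have been caused by the".

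SAP section 8.6.1 assigns TEAEs from Day 15 dosing onward to LOXO-305 plus cocktail and gives no end point.

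**The concern.** The secondary objective is the safety and tolerability of multiple LOXO-305 doses. While all AEs are recorded, subjects live in the unit and have little community exposure. When they go home, recording narrows to events judged related. For a risk that would show itself as infection, the narrowing comes when exposure resumes.

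The filter then depends on a causality judgement whose definitions do not fit together. Whether a cold or a mild COVID-19 case enters the database could turn on which sentence of Appendix 1 the investigator applies.

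The analysis inherits the problem. The TEAE column for LOXO-305 plus cocktail combines days on which every AE counts with days on which only related AEs and SAEs count, and nothing in the SAP tells the reader so.

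**Working it through.** The plan gives no figure to reproduce. The check is of the text, with simple arithmetic for the window.

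**1. Length of the related-only window (completers).** Inputs: last LOXO-305 dose on Day 19, EOT on Day 23, call at 7 ± 2 days after EOT (section 3.1).
- Call day: 23 + 5 = Day 28 to 23 + 9 = Day 32, nominally Day 30.
- Window: 5 to 9 days, ending 28 − 19 = 9 to 32 − 19 = 13 days after the last dose.
- In 16 subjects: 16 × 5 = 80 to 16 × 9 = 144 subject-days, nominally 16 × 7 = 112.

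**2. Share of the SAP column affected.** All-cause recording under LOXO-305 plus cocktail runs from Day 15 to Day 23, which is 8 days. The related-only share of the column's follow-up is:
- shortest: 5 / (8 + 5) = 38%
- nominal: 7 / (8 + 7) = 47%
- longest: 9 / (8 + 9) = 53%

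**3. Appendix 1 applied to a non-serious infection after release.** Crossing the two conditions gives four cases:

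| Time course | No other cause identified | Another cause identified or suspected |
|---|---|---|
| Consistent with causality | RELATED | neither definition met |
| Rules out causality | neither definition met | NOT RELATED |

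An infection a few days after release, with a known contact, plausibly falls in the top right cell. It fails RELATED because another cause can be named. It fails NOT RELATED because the time course does not exclude the drug. The reasonable-possibility sentence could lead an investigator to call it related, but that sentence defines association with the drug, while the recording rule turns on RELATED. The event may therefore be recorded or not.

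**4. Is there another route into the database?** SAEs are reported whatever the relationship. Volunteered non-serious reports meet the same filter. SAP section 8.6.1 counts a TEAE with missing relationship as related, but this cannot help an event that was never entered. Scheduled haematology ends on Day 22 (Appendix 4 footnote o). No other provision records a non-serious AE that is not assessed as related.

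**5. Upper bound on lost records.** The documents give no background AE rate. Assuming 0.01 to 0.05 AEs per subject-day over the nominal 112 subject-days, 112 × 0.01 = 1.1 to 112 × 0.05 = 5.6 AEs would arise. This is an upper bound under that assumption: it counts all AEs, not infections alone, and treats none as related or serious.

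**The case against.** The strongest reply is that the named risk is measured directly. A white-cell differential is scheduled at Screening, Check-in and Days 2, 6, 12, 15, 17, 20 and 22, is summarised as change from baseline (SAP section 8.6.2) and is reviewed before discharge. All-cause AE recording continues for 96 hours after the last dose. With up to 16 subjects, no concurrent control and a changed environment after release, a few colds could not be attributed to drug or to background. The rule is also consistent across the documents, so it is a deliberate choice. All of this stands, and it is why the gap is modest.

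A reader might infer that Appendix 1 flatly bars any infection with an identified cause from being RELATED. The documents do not support that. The examples of other causes are drugs, therapies, complications and comorbidities; a pathogen or contact is not among them. NOT RELATED is equally hard to satisfy. Section 1.4.1 reports a septic shock with a named organism that was judged related in the patient study, although that study's causality definition is not given. The definition is inconsistent; it is not a clear bar.

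A reader might also infer that the safety tables would show no infections after release whatever happened. That is wrong: serious infections, and non-serious ones judged related, are still reported.

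Nor can the gap be sized from the half-life of about 20 hours. Residual drug at release bears on discharge timing, not on which events are recorded, and the documents give no white-cell recovery time.

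What survives is that non-serious events not assessed as related are lost just after confinement ends, and that the SAP does not separate the two regimes.

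**Conclusion.** The point holds as a modest gap that is cheap to close. For 5 to 9 days after release, a non-serious AE is recorded only if assessed as related, and for an infection that assessment is not well defined. Such an event may go unrecorded; the text does not establish that it will.

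The firmer consequence lies in the SAP: 38% to 53% of a completer's follow-up in the LOXO-305 plus cocktail column is under a narrower recording rule, so a low count there cannot be read as all-cause incidence. These shares assume completion on Day 23 and a call within its window. The filter also applies after ET, over the same 5 to 9 days. Any number of lost AEs rests on an assumed background rate and is an upper bound.

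**What to change.** 1. **Recording rule.** In the synopsis, section 3.1, section 7.3.1, Appendix 4 footnotes j and v, and SAP section 4, state that all AEs with onset from EOT or ET through EOS, whether elicited at the follow-up call or volunteered, are recorded regardless of relationship, with relationship then assessed. Reword the stated purpose of the call in section 7.3.1 and footnote v to match.
2. **Analysis.** In SAP section 8.6.1, end the LOXO-305 plus cocktail assignment at EOT or ET and show later-onset AEs in a separate column or listing. This also avoids adding all-cause post-release events to the on-treatment column.
3. **Causality wording.** Reconcile RELATED, NOT RELATED and the reasonable-possibility sentence in Appendix 1, so that every event falls into exactly one category. Without this step, a recorded infection would still be classified inconsistently.

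The cost is a protocol amendment through the IRB, matching SAP text, a few extra non-serious AE records to code and one more column or listing. No visit, sample or procedure is added.
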